5.3.1 Number of Participants

Number of participants: 100 total, 50 in each group GoGoband®, SNEA,

Number to be screened: 200

5.3.2 Eligibility Criteria/Vulnerable Populations

In order to be eligible to participate in this study, an individual must meet all of the following criteria:

1. Provision of signed and dated informed consent form
2. Stated willingness to comply with all study procedures and availability for the duration of the study

3. Male or female, aged 6 to 21 years
4. In good general health as evidenced by medical history and diagnosed with MNE
5. Ability to and be willing to adhere to the treatment regimen.
6. Subjects to be eligible for the Trial need to have functioning WiFi at home utilizing a home network and not a cellular tethering connection.

An individual who meets any of the following criteria will be excluded from participation in this study:

1. No patient may have had treatment of MNE in the past 6 months whether with medications or alarms
2. Current use of on ADHD medications, Tricyclics, SSRI's, NRI's or any antipsychotic medications.
3. Presence of Autistic Spectrum disorder, ADHD, genetic syndrome associated with developmental or learning disabilities
4. Treatment with another investigational drug or other intervention within last 6 months
5. Any form of Diabetes Mellitus or Diabetes Insipidus
6. No patient with known Chronic renal disease with moderate to severe renal impairment (defined as a creatinine clearance below 50mL/min).
7. No patient with known hyponatremia or a history of hyponatremia.

6 Methods

6.1 Treatment – Device

6.1.1 Intended Use for Device (provide the following information for each device being investigated in the study)

Generic bedwetting alarms

Generic bedwetting alarms which are commercially available and are an FDA class II device
See below the FDA documentation on enuresis alarms

[Code of Federal Regulations]
[Title 21, Volume 8]
[Revised as of April 1, 2020]
[CITE: 21CFR876.2040]

TITLE 21--FOOD AND DRUGS
CHAPTER I--FOOD AND DRUG ADMINISTRATION
DEPARTMENT OF HEALTH AND HUMAN SERVICES
SUBCHAPTER H - MEDICAL DEVICES

PART 876 -- GASTROENTEROLOGY-UROLOGY DEVICES

Subpart C - Monitoring Devices

Sec. 876.2040 Enuresis alarm.

(a) *Identification.* An enuresis alarm is a device intended for use in treatment of bedwetting. Through an electrical trigger mechanism, the device sounds an alarm when a small quantity of urine is detected on a sensing pad. This generic type of device includes conditioned response enuresis alarms.

(b) *Classification.* Class II (special controls). The device is exempt from the premarket notification procedures in subpart E of part 807 of this chapter subject to § 876.9.

[48 FR 53023, Nov. 23, 1983, as amended at 63 FR 59228, Nov. 3, 1998]

GoGoband® is a FDA class II device

GoGoband® is a biometric, artificial intelligence and machine learning powered wearable bedwetting alarm uses of heart rate data, heart rate variability (HRV) analysis and real time monitoring that combines the use of algorithms developed with machine learning to learn the individual profile of each patient. Each device consists of a photoplethysmography (PPG) heart rate sensor worn on the calf, a beside tablet, a Bluetooth moisture sensor and a parent app that can alarm the parent that a wetting event is eminent or has occurred.

6.1.2 Device Administration and Schedule

SNEA: Device Will be provided to the patient

1. Instruction will be provided on how to set up the device and use it
2. The device will be worn consecutively for 3 months.
3. The alarm use will be terminated if they have been dry for 3 months consecutively.

GoGoband®: Device Will be provided to the patient

1. Instruction will be provided on how to set up the device and use it
2. The device will be worn consecutively for 3 months
3. The device will follow the built in algorithm in the device to decide when to begin the weaning process.
4. The weaning process will occur automatically until there no more nights in which the system will sound impending urination alarms

Non-compliant patients will be removed from the study. Alarms will not be requested back from the participants.

Reasons for noncompliance will be the following

1. Not taking medication
2. Not using device
3. Not filling in and submitting biweekly logs.

If a bedwetting alarm breaks or is nonfunctional the device will be replaced, and the study will proceed from the last active day

Method of Assignment/Randomization (if applicable)

2000031281

February 20, 2024

Randomization will be accomplished by having 100 envelopes with 50 SNEA and 50 GoGoband® choices. The envelopes will be distributed to the sites and pulled randomly at each site.

Age matching:

After 50% enrollment in any group the average age and standard deviation of the group will be calculated and an effort to adjust enrollment so groups are age matched will be made.

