Randomized Study Of Novel Enuresis Alarm (GoGoband®)Vs Standard Bedwetting Alarm

Protocol Number
2000031281

NCT05214131

Protocol Version
February 20, 2024
Version #6

IDE Number:

IDE Holder:

PRINCIPAL INVESTIGATOR:

[name]., Ph.D.
Department of Urology
[contact]
Email Address: [contact]

Confidentiality Statement:

2000031281

February 20, 2024

REVISION HISTORY:

Include the IRB approved protocol version number and date for each revision of the protocol. All version history should remain in the table and never be deleted. The oldest IRB approved version of the protocol should be listed on the top row. The most recent IRB approved version should be listed on the bottom row.

Revision #	Version Date
1	Sept 1 2021
2	Sept 9 2021
3	November 18, 2021
4	December 28, 2021
5	Jan 15 2022
6	February 20, 2024

2000031281

February 20, 2024

Synopsis

Primary Objective
 
Identify the dry night rate in patients using the GoGoband® nocturnal enuresis device vs a standard Pflaunger bedwetting alarm.

Secondary Objective (if applicable)
 
to ascertain if familial incidence of nocturnal enuresis has an effect on outcomes

Study Duration: total 3 years, 2 years active with 1 year for analysis

Study Design
 
Include a high-level description of the study design.
 
This is a prospective randomized comparison of GoGoband® vs standard nocturnal enuresis alarm

Number of Study Sites
 
Study sites will include all clinic sites where patients are seen in the Yale New Haven Health System
 
Yale New Haven Children’s Hospital clinic WP2 Yale New Haven Children’s Hospital Longwharf Clinic Yale New Haven Children’s Hospital Trumbull clinic Yale New Haven Children’s Hospital Norwalk clinic Yale New Haven Children’s Hospital Greenwich Clinic

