3.2.5 Biomarkers (if applicable)

3.3 Study Procedures

3.3.1 Study Schedule

Total study time is 3 months exclusive of prestudy visit which should be within 2 months of start of study.

Prestudy entry:

- all Nocturnal enuresis patients are all evaluated with physical examination and post void residual check.
- DVQ questionnaire is administered
- Inclusion and exclusion criteria evaluated
- treated with standard urotherapy previously described.

Visit 1:

- Confirm that patient has no daytime voiding symptoms identifying patient has MNE and qualifies for study
- Offer the patient treatment Choices:

2000031281

February 20, 2024

- medical treatment if so no longer candidate for study
- Alarm therapy: If Alarm therapy is chosen: randomize into SNEA or GoGoband®
- Consent to be signed
- Dispense alarm that day or have patient return within a week to have the alarm demonstrated and how to setup and to take home.
- Subject log is given along with alarm.

Visit 2:

- 1 month virtual or in person to follow progress,
- log is handed in, scanned into my chart, faxed or emailed
- new log dispensed

Visit 3:

- 2 month virtual or in person to follow progress
- log is handed in, scanned into my chart, faxed or emailed
- a new log dispensed

Visit 4:

- 3 months virtual or in person to close out study,
- log is handed in, scanned into my chart, faxed or emailed.
- Patients are informed that they can keep the alarm and continue to use it if they wish.

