3.3.4 Enrollment

The person performing the initial screening and evaluation of the patient will be the person in charge of enrolling the patient

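### Arms are assigned by an unordered pull of envelopes at each clinic, with no safeguard against selecting or re-drawing an assignment, no record that would show it, and no assurance of balance within clinic

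*Combined protocol and SAP*

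**What the plan says.** Two sentences in the randomisation paragraph (under 6.1.2 Device Administration and Schedule) give the whole method: "Randomization will be accomplished by having 100 envelopes with 50 SNEA and 50 GoGoband® choices", followed by "The envelopes will be distributed to the sites and pulled randomly at each site". The count agrees with 5.3.1 ("Number of participants: 100 total, 50 in each group"). The Synopsis names five clinics. The same paragraph adds that, once either group is half enrolled, ages will be compared and "an effort to adjust enrollment so groups are age matched will be made"; how this would be done is not stated.

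On roles, 3.3.4 Enrollment says: "The person performing the initial screening and evaluation of the patient will be the person in charge of enrolling the patient". On order, the Visit 1 list in 3.3.1 Study Schedule has "If Alarm therapy is chosen: randomize into SNEA or GoGoband" and, as its next item, "Consent to be signed".

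On outcome data, families in both arms keep a nightly log (3.2.1 Efficacy). The GoGoband system also stores wet/dry events automatically (5.1, item 7; 4.6). No automatic record is described for SNEA.

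No other section adds a generated sequence, numbering, sealing, an opening log, a named holder, blocking or stratification. The appendices are listed by title only in the text available (flowchart, alarm log, recruitment email, prescreening questions), and none of the titles suggests a randomisation procedure.

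**The concern.** Randomisation protects a comparison only if the person admitting a child cannot influence which arm follows, and if the record can later show this. Here no envelope is linked to a child before it is opened. An envelope could be opened, returned or set aside and another drawn, and nothing in the described procedure would reveal it.

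Three features of this trial raise the stakes. The devices look different, so past assignments are known; staff who knew a clinic's starting mix could work out what remained. The plan's own pilot data (2.1.2) associate higher compliance with more dry nights, so directing motivated families to one arm would bear directly on the outcome. The age-matching intention gives staff a reason to think about arm when enrolling, and with an unordered stock such an adjustment could not be told apart from selection.

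A lesser matter is that the 50:50 split is fixed only over all 100 envelopes, so nothing guarantees similar arm numbers within a clinic.

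**Working it through.** **The plan's own figure.** The plan gives no figure for concealment or balance. The nearest is the sample size in 3.4.2 (0.5 v 0.8, one-sided 5%, power 0.8). With unpooled variance: (0.25 + 0.16) × (1.645 + 0.842)² / 0.30² = 28.2, rounded up to 29, which matches the stated 29 if read as per arm. The point does not depend on it; it shows only that 50 per arm leaves room for small departures from equal totals.

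**What the text supplies.**
- Generated sequence or fixed order: none; the draw is at random from the clinic's envelopes.
- Envelopes numbered, opaque or sealed: not described.
- Child identified on the envelope before opening: not described.
- Person who holds or pulls the envelopes: not named.
- Separation of screening from enrolment: none (3.3.4).
- Consent clearly before assignment: no; the Visit 1 list has the reverse order (3.3.1).
- Opening log or reconciliation: not described.

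**Chance imbalance within clinic (illustration).** Assumption: the 100 envelopes are shuffled and 20 go to each of five clinics. The documents give neither clinic sizes nor the mix sent to each. The number X of GoGoband envelopes at a clinic is then hypergeometric, P(X = k) = C(50,k) × C(50,20−k) / C(100,20).
- SD = √(20 × 0.5 × 0.5 × 80/99) = 2.01.
- 13:7 or worse (X ≤ 7 or X ≥ 13): 0.211.
- 14:6 or worse: 0.078.
- At least one of five clinics, from 100,000 simulated shuffles: 13:7 or worse 0.639; 14:6 or worse 0.311.

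If each clinic instead received 10:10, full use would balance it exactly. If only 10 of the 20 were used, a difference of 4 or more would have probability 0.18.

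**What chance imbalance could do.** Suppose one clinic is 13:7, totals stay 50:50, and its success rate differs from the rest by 20 points (assumed). The shift in the arm difference is (13/50 − 7/50) × 0.20 = 0.024, or 2.4 points, against a planned 30.

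**What steering could do (illustration).** Assume no true effect and a fraction f of children steered, those with success rate 0.7 to GoGoband and those with 0.3 to SNEA, all others at 0.5. The arm rates become 0.5 + 0.2f and 0.5 − 0.2f. With 50 per arm and a one-sided 5% test, the rejection rate is:
- f = 0.1 (0.52 v 0.48): about 11%;
- f = 0.2 (0.54 v 0.46): about 20%;
- f = 0.3 (0.56 v 0.44): about 33%.

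The documents give no basis for any value of f, including zero.

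**The case against.** The strongest reply is that a random pull, carried out as written, does not reveal the next assignment. Returning an envelope and drawing again would depart from the procedure, not follow it. That is correct. A reader might infer that the method itself exposes assignments, and the text does not support this. What stands is that a departure is not prevented and would leave no trace.

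Other stronger readings also go too far.
- A reader might infer that the screener holds the envelopes and makes the draw. The documents say only that the screener enrols; they name nobody for the draw.
- A reader might infer that arms will be unbalanced within clinics. An equal split per clinic is compatible with the text; it is simply not required.
- A reader might infer confounding by clinic staff or local population. The clinics belong to one health system, participants come from one continence programme, and no such differences are described. Chance imbalance adds variability rather than systematic bias, and the 2.4-point example is small.
- A reader might infer that all outcomes are family-reported. GoGoband events are also recorded automatically, so sole reliance on family logs applies to SNEA.
- A reader might infer that children are randomised without agreement. 5.1 has families asked whether they wish to take part, and the Visit 1 list may not be chronological. The order is nonetheless left unclear, and it matters for concealment.

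Small departures from 50:50 overall are not a serious problem, given 29 needed and 50 planned per arm.

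**Conclusion.** The concern holds as a gap in concealment and audit trail. The stated method is an unordered draw, without a fixed sequence, without a named independent person, and without any record that could show assignments were not chosen. It affects every child from the first, and no later analysis can detect or undo selection at assignment. The documents do not show that selection will occur, and its size cannot be derived from them; the 11% to 33% rejection rates rest wholly on assumed steering.

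Within-clinic balance is secondary. The 21% for a given clinic and about 64% for at least one depend on an assumed random deal of 20 envelopes to each of five clinics. They describe chance imbalance, not the main risk.

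**What to change.** Amend the randomisation paragraph as follows.
- Use a pre-generated list in randomly varying permuted blocks, preferably stratified by clinic, prepared by someone with no part in enrolment. Keep block sizes from clinic staff, since assignments are visible.
- Release assignments through a central or electronic system if one is available. Otherwise use opaque, sealed, sequentially numbered envelopes opened strictly in order.
- State that assignment follows signed consent and confirmed eligibility, and reorder the Visit 1 list in 3.3.1 to match.
- Write study number, date and time on each envelope before opening, and reconcile all envelopes, opened and unopened, at close-out.
- Reconcile the age-matching intention with a fixed sequence, so that it cannot override the list.
- Settle the list length: 100 envelopes fit 5.3.1 but not the 150 participants in the Synopsis.

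The cost is one list and one amended paragraph, with no change in sample size. Final totals may differ by a few children from exactly 50:50 where clinics end mid-block. With blocks of 2 and 4, for example, the difference within a clinic cannot exceed 2. Over five clinics it cannot exceed 5 × 2 = 10, and only if every clinic ended unbalanced in the same direction.

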3.4.3 Planned Analysis

3.4.3.1 Primary Analyses

Outcomes will be evaluated between the 2 groups using crosstab analysis of the data for the following data :

Wetting event: Dry or Wet

Did patient wear the device: yes or no used to measure compliance

Did patient take the medication: yes or no used to measure compliance
 Is the patient considered cured (dry 29/30 nights) : yes or no
 Is the patient partially better (improvement of 50% or more compared to pretreatment)
 Does the patient show no improvement (<50% improvement compared to Pretreatment)
 Logistic regression analysis may be performed on the incremental wet dry data vs time to achieving dryness

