3.4.3.4 Analysis of Subject Characteristics

Age and sex of patients in each group
 Dvq scores of each group

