3.4.3.5 Interim Analysis (if applicable)

interim analysis will be done a midpoint to evaluate ages of groups so we can make adjustments to have an age matched cohort.

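### The mid-trial age-matching rule has no algorithm or random element and can undermine random allocation for about half of the trial

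*Combined protocol and SAP*

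**What the plan says.** Section 6.1.2 (Method of Assignment/Randomization) provides 100 envelopes, 50 per device, with no age strata: "The envelopes will be distributed to the sites and pulled randomly at each site". Its age-matching paragraph sets a trigger of 50% enrolment in any group. At that point the group's mean age and standard deviation are calculated, and then "an effort to adjust enrollment so groups are age matched will be made". Section 3.4.3.5 restates this: "interim analysis will be done a midpoint to evaluate ages of groups so we can make adjustments to have an age matched cohort".

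Other relevant text:

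- Size, section 5.3.1: "Number of participants: 100 total, 50 in each group". The Synopsis gives 150 instead.
- Enrolment, section 3.3.4: "The person performing the initial screening and evaluation of the patient will be the person in charge of enrolling the patient".
- Primary analysis, section 3.4.3.1: "Outcomes will be evaluated between the 2 groups using crosstab analysis of the data for the following data". No covariate is named, and the Subsets and Covariates heading (3.4.4) has no text under it.
- Section 3.4.3.4 lists "Age and sex of patients in each group" as descriptive characteristics, so age will be on file.

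Nothing in the plan states how the adjustment is made, how large an age gap prompts it, who decides, or what happens to the unopened envelopes.

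**The concern.** A randomised comparison is sound because nothing about a child influences which arm the child receives. The age-matching rule asks someone to look at the composition of the arms and then act to change it, without saying how.

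One reading is harmless: staff change which ages they recruit, and an envelope still decides the arm. That keeps allocation random but gives no means of moving one arm's mean age relative to the other. To bring the arms together actively, age has to be tied to arm by overriding, redrawing or steering envelopes, or by choosing whom to enrol once the next arm is known. The text neither requires nor rules out any of these.

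Age balance is not the problem. The danger is that a discretionary choice made for age also follows severity or expected compliance, and matching on age does nothing for those factors. The primary analysis is unadjusted, so any such difference would pass straight into the device comparison. Adjusting for age afterwards would not remove it.

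**Working it through.** The plan gives no figure of its own for this rule. The sample-size calculation in 3.4.2 does not enter, except that its SNEA proportion of 0.5 is borrowed in step 3.

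**1. How much of the trial follows the look.** Inputs: 50 per arm (5.3.1) and a trigger of 50% in any group (6.1.2), so 25 in one arm.

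- The other arm then holds 0 to 24, so the places left run from 100 − (25 + 24) = 51 to 100 − (25 + 0) = 75.
- Simulated random orders of 50 + 50 envelopes give a median of 54 left, with a 95% range of 51 to 61. The upper limit of 75 is only theoretical.
- At a literal midpoint (3.4.3.5), 50 are left.
- At the Synopsis total of 150 (75 per arm, trigger 38), 150 − (38 + 37) = 75 to 150 − 38 = 112 are left.

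**2. What binding envelopes can do about an age gap.** Let D be the difference in mean age at 25 per arm. The final difference at 50 per arm is (D + D_later) / 2.

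- If the envelopes stay binding, the expected D_later is 0, so the expected final gap is D/2.
- To close the gap fully, D_later must equal −D: the later 25 per arm must differ in age by arm, in the opposite direction.
- Some gap is to be expected by chance. The SE of D is SD × √(2/25). The documents give no age SD. Assumed SDs of 2.5, 3.0 and 3.5 years give 0.71, 0.85 and 0.99 years.

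**3. What prognostic selection would do to the result (illustration; inputs assumed).** Suppose no device effect, 50 per arm, and cure probability 0.5. That value is borrowed from 3.4.2, which does not label it a cure rate. Discretion raises cure probability by a shift s in the last 25 GoGoband children only. The bias in the difference is (25/50) × s. The false-positive rate comes from exact enumeration of the pooled two-proportion z test.

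| Shift s | Bias (points) | One-sided 5% test | Two-sided 5% test |
|---|---|---|---|
| 0 | 0 | 4.5% | 5.7% |
| 0.05 | 2.5 | 7.4% | 6.4% |
| 0.10 | 5 | 11.6% | 8.7% |
| 0.20 | 10 | 24.5% | 18.1% |

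A different assumed mechanism points the same way. Here the last 52 of 100 children are allocated by judgement, and a binary prognostic factor shifts response by ±20 points. If a favourable child goes to one particular arm with probability 0.6, 0.7 or 0.8, the one-sided error for a test favouring that arm is about 9%, 17% or 28%. With a ±10-point factor it is about 6%, 9% or 13%. With probability 0.5, meaning no selection, it stays at about 4.5%.

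**The case against.** The strongest reply is that the harm needs two steps the plan never states: staff must link age to arm, and that choice must also follow prognosis. The plan promises only an effort, does not define age matched, and nowhere says the envelopes are set aside. This stands as a limit on what can be claimed. The documents show that allocation can be compromised, not that it will be. It does not rescue the rule, because actively matching the arms gives exactly that discretion and nothing in the text constrains it.

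The illustration also assumes a direction. If the shift lowers cure in the GoGoband children instead, the one-sided false-positive rate falls to 2.6%, 1.4% and 0.3%. If both arms rise by 0.10 it stays at 4.5%. This is correct: nothing in the rule says which arm would gain. The two-sided inflation is the same in either direction.

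Stratified blocks begun after the look would likewise leave about D/2 of an existing gap. That also stands, but a random rule leaves a small chance imbalance that a model can handle, whereas a discretionary one leaves a bias of unknown source.

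Finally, having the same person screen and enrol does not prove that this person sees the next envelope. That is fair. It removes a possible safeguard but is not evidence of a breach, and the main point does not depend on it.

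**Conclusion.** The concern holds and should be fixed before further allocation. The plan contains a mid-trial rule that puts unspecified discretion into allocation for about half of the trial: about 54 of 100 places under the 6.1.2 trigger, or 50 at a literal midpoint. No other section supplies a procedure or a protective analysis.

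The size of any bias cannot be derived from the documents. On the assumed shifts it is 2.5 to 10 percentage points, with a one-sided false-positive rate of 7.4% to 24.5% when selection favours GoGoband. It is nil if selection is unrelated to prognosis. The count of remaining places and the halving of an early gap need no assumption beyond 50 per arm and random drawing.

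A secondary point does not affect this conclusion. The Visit 1 list in 3.3.1 places randomisation before "Consent to be signed", while 5.3.2 makes signed consent an eligibility criterion. The list may not be meant as a sequence, but the two should be reconciled.

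**What to change.** - Delete the age-matching paragraph in 6.1.2 and the age adjustment in 3.4.3.5. Run the 1:1 envelopes unaltered to the end.
- Prespecify a logistic model for cure with arm and age, reported beside the crosstab. This is a new analysis: 3.4.3.1 now only allows for an optional logistic regression of wet/dry data against time.
- If balance by design is wanted, use sealed, sequentially numbered blocks, prepared in advance and stratified by age band, for the remaining allocations.
- If any adjustment has already been made, document when, by whom and for which children.
- Reorder the Visit 1 list in 3.3.1 so that consent clearly comes before the envelope is opened.

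The cost is a short amendment and one added model using data already collected, with no extra patients or visits. Some chance age imbalance may remain, and the model deals with it.
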